12.1 Primary Endpoint

[Redacted text block for Primary Endpoint]

12.2 Secondary Efficacy Endpoints

[Redacted text block for Secondary Efficacy Endpoints]

[Redacted text block]

[Redacted text block]

[Redacted text block]

|

[Redacted text block]

13 Safety Analysis

The safety population will be used for all safety analyses. All recorded safety parameters will be listed by treatment, subject ID and visit or visit date.

13.1 Adverse Events

The investigator will promptly review each Adverse Event (AE) for accuracy and completeness, and classify each AE according to its intensity, its relationship to study drug or administration procedure, and its seriousness. AEs will be coded using version 22.0 of the MedDRA dictionary. AEs will be monitored throughout the study and documented on the appropriate AE form. AEs will be categorized as ocular and non-ocular events as well as by system organ class (SOC) and preferred term (PT), seriousness, severity, and relation to study medications.

All treatment-emergent adverse events (TEAEs) will be summarized. A TEAE is defined as an AE that is new or worsened in severity compared to the first dose of study drug. All AEs will be presented in data listing with a flag indicating the event is a TEAE.

TEAEs will be summarized by subject. In addition, the number of TEAE episodes that occurred during the study will be provided in the overall summary of AE table.

The following presentations of TEAEs will be generated:

- Overall adverse events summary (including any TEAEs, ocular TEAEs, resolved ocular TEAEs, non-ocular TEAEs, ocular TEAEs, non-ocular TEAEs, SAEs, treatment-emergent SAEs, treatment-related treatment emergent SAEs, TEAEs by maximum severity, TEAEs by relationship to study drug, AEs leading to treatment/study discontinuation);
- Serious adverse events (SAE) by SOC and PT;
- All ocular TEAEs by SOC and PT;
- All non-ocular TEAEs by SOC and PT;
- TEAEs leading to treatment discontinuation.
- TEAEs leading to study discontinuation.

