## 9 SAFETY DEFINITIONS, SAFETY MONITORING AND REPORTING

### 9.1 Adverse Event

An adverse event (AE) is defined as any untoward medical occurrence associated with the use of a drug in humans, whether or not the event is considered drug-related. An AE can therefore be any unfavorable and unintended sign (e.g., an abnormal laboratory finding), symptom, or disease occurring after the subject started dosing with the study drug, without any judgment about causality. Any pre-existing medical condition that worsens after administration of the study drug will also be considered a new AE.

Study drug includes the investigational drug under evaluation and placebo.

AE collection will start following the first administration of study drug until the last follow up visit of the study.

Documentation regarding the AE should be made as to the nature, date of onset, end date, severity, relationship to study drug, action(s) taken, seriousness, and outcome of any sign or symptom observed by the Investigator or reported by the subject upon indirect questioning.

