#### 10.5.6 Safety Analysis

All safety analyses will be performed on the safety population.

The safety of OC-01 (varenicline) will be assessed primarily by the incidence of AEs. An AE will be considered a treatment-emergent AE (TEAE) if it occurs or worsens on or after initiation of treatment. An overall summary of TEAEs will be presented including the number of events and the number of subjects with events (along with percentages) by treatment group for TEAEs in several categories base on seriousness, relationship to treatment, and severity.

Other safety endpoints including visual acuity, slit-lamp biomicroscopy and intranasal examination will be summarized by treatment group and visit using descriptive statistics. Changes or shifts from baseline will be summarized where appropriate. For assessments performed by eye, study eye and fellow eye will be summarized separately.

The SAP will present methods of analysis of these defined parameters in detail.

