9.4 Definition of Study Day or Dosing Day

Study and dosing days are defined as follows:

Study Day = [Event date – Randomization date + 1] if after randomization
[Event date – Randomization date] if before randomization

Dosing Day= [Event date – First dosing date + 1] if after first dosing date
[Event date – First dosing date] if before first dosing date.

Note that with the definition above, days of "0" will not be used.

For subjects whose reference date is missing, the study day will also be categorized as missing.

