9.11 Treatment Exposure

Each randomized subject will receive an application of OC-01 (varenicline) Nasal Spray or placebo twice daily (BID) for 28 days. Duration of exposure to study treatment, in days, will be summarized for all randomized subjects. Summary statistics for duration of exposure will be presented by visit and treatment group.

10 Ocular Assessments

[figure not shown]
Ocular assessments will occur at baseline and post-baseline study visits. The results, grade, clinical significance, and relatedness to administration procedure and study drug, will be listed, summarized in tables, and presented in figures as appropriate.

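### Treatment-emergent adverse events have no on-treatment cut-off and no split by period, so the headline summaries pool 28 days of dosing with about 308 days off drug

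*SAP*

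**What the plan says.** SAP Section 13.1 gives the definition: "A TEAE is defined as an AE that is new or worsened in severity compared to the first dose of study drug". Protocol Section 10.5.6 counts an adverse event as treatment-emergent "if it occurs or worsens on or after initiation of treatment". The two agree, and neither states an end.

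The end is set in practice by collection. Protocol Section 9.1: "AE collection will start following the first administration of study drug until the last follow up visit of the study". That visit is Visit 7, Day 336 ±7, in the schedules of both documents. On dosing, SAP Section 9.11 says: "Each randomized subject will receive an application of OC-01 (varenicline) Nasal Spray or placebo twice daily (BID) for 28 days".

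The TEAE presentations in SAP Section 13.1 are readable. They break events down by ocular or non-ocular type, system organ class and preferred term (SOC/PT), seriousness, maximum severity, relationship, and discontinuation. Episodes are counted over the whole study. No presentation is split into on-treatment and follow-up. Timing appears only in listings: "All AEs will be presented in data listing with a flag indicating the event is a TEAE" and, in SAP Section 13, "All recorded safety parameters will be listed by treatment, subject ID and visit or visit date".

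Protocol Section 10.5.6 says that safety "will be assessed primarily by the incidence of AEs".

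**The concern.** The main safety measure is an incidence, and the period over which it is counted is about twelve times as long as dosing (336/28 = 12). A subject with a cold in month eight and a subject with an event on Day 3 both count once in the any-TEAE row. The summary tables would not show which events arose while the subject was taking study drug.

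What is at stake is how well the safety tables describe exposure to the drug. If an active arm adds events only during dosing, and ordinary events accumulate in every arm over the next 44 weeks (308/7 = 44), the arms move closer together in the pooled rows. Severity is affected in the same way, because a subject's maximum severity may come from an off-drug event. The listings let a reader recover timing subject by subject, but the TEAE flag does not mark the period, and a listing is not an incidence by arm.

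**Working it through.** **Inputs.** Dosing 28 days (SAP 9.11). Visit 4 at Day 28 ±4 (Protocol 8.3.1). Participation of about 48 weeks (Protocol 8.8). Visit 7 at Day 336 ±7 (Appendix 1 of both documents).

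**Plan's own figure.** 48 × 7 = 336 days, as Protocol 8.8 states.

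**Off-drug share, for a subject followed to Visit 7.** Share = (last visit day − last dosing day) / last visit day.
- Nominal: (336 − 28)/336 = 308/336 = 91.7%.
- Lowest across the visit windows: (329 − 32)/329 = 297/329 = 90.3%.
- Highest: (343 − 24)/343 = 319/343 = 93.0%.

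Early treatment stoppers are asked to stay in safety follow-up (Protocol 8.6.3), so their share is higher. Subjects lost before Visit 7 have a lower share.

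**Which outputs are exposed.**
- Mixed: any TEAE, TEAEs by maximum severity, and preferred terms that are common in the background.
- Partly protected: rows by relationship to study drug, which the investigator judges masked (Protocol 9.1.2).
- Little or not affected: terms tied to dosing with little background (the protocol describes sneezing in ONSET-1 in this way); TEAEs leading to treatment discontinuation; visual acuity, slit-lamp and intranasal findings, which Protocol 10.5.6 summarises by visit; and efficacy.

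**How dilution would work (illustration only; every rate is assumed).** Let r be a constant background rate of first events per person-year and e an added risk confined to dosing, with no dropout. Placebo risk to day d is p0 = 1 − exp(−r·d/365.25). Active risk is p1 = 1 − (1 − p0)(1 − e). The risk difference is then e·exp(−r·d/365.25), and the 336-day difference divided by the 28-day difference is exp(−r·308/365.25), whatever the value of e. If only half of events are captured after Day 42, the exponent uses 14 + 294/2 = 161 days in place of 308.

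| Assumed r | Ratio, full capture | Loss | Ratio, half capture | Loss |
|---|---|---|---|---|
| 0.02 | 0.983 | 2% | 0.991 | 1% |
| 0.05 | 0.959 | 4% | 0.978 | 2% |
| 0.25 | 0.810 | 19% | 0.896 | 10% |
| 0.5 | 0.656 | 34% | 0.802 | 20% |
| 1.0 | 0.430 | 57% | 0.644 | 36% |

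For example, with r = 0.5, e = 0.10 and full capture, 13.4% against 3.8% at 28 days (9.6 points) becomes 43.2% against 36.9% at 336 days (6.3 points). The effect is trivial for rare terms and can be large for an any-event row. The documents do not say where this trial lies in that range.

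**The case against.** The strongest reply is that nothing here conflicts or fails. Protocol and SAP use the same open-ended definition, the long-term visits are deliberate, and an open window keeps late events in view. All arms have the same planned follow-up. Relationship is judged masked and has its own rows, ocular and nasal examinations are reported by visit, and dated listings exist. At the low rates that may suit many single preferred terms, the illustrated loss is 1% to 4%.

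Most of this stands. It is a good reason to keep the whole-study tables and to limit what is added. It does not remove the gap: relationship is an investigator's judgement, whereas onset date is a recorded fact, and neither the by-visit examinations nor the listings give incidence by arm during dosing.

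A reader might go further and infer three things that the documents do not support.
- *That the two TEAE definitions contradict each other or are wrong.* They agree, and an open end is a legitimate choice.
- *That the safety comparison loses power or validity.* No between-arm test of adverse events is stated in the readable text, so any power figure would rest on assumed rates and on a test that is not stated in it.
- *That follow-up events are confounded by treatments allowed again after Day 28.* No such use is shown, and concomitant medications are recorded at Visits 5 to 7.

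**Conclusion.** The point holds as a reporting gap. The TEAE window has no end, no readable summary is split by period, and 91.7% of the planned window (90.3% to 93.0%) is off drug. This share rests on planned visit days and on follow-up to Visit 7. It does not allow for dropout.

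The consequence is conditional. Dilution of on-drug differences needs added risk that is concentrated in dosing and background events that are common, and its size cannot be derived from the documents. The cost is a less interpretable description in the any-TEAE, severity and common-term rows, not a lost inference. The gap is worth closing because these rows carry the stated primary safety measure and the data needed are already planned.

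**What to change.** Before unmasking, pre-specify in SAP Section 13.1, and align in Protocol Section 10.5.6:

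1. An on-treatment period from first dose to each subject's actual last dose plus an interval that the sponsor defines and justifies. Follow-up is the time after that, to Visit 7.
2. Assignment of each event by onset date relative to the first-dose and last-dose dates. Dosing Day in SAP Section 9.4 counts from first dose only and cannot locate the end of treatment, least of all for early stoppers. Take last dose from the exposure data behind SAP Section 9.11.
3. A rule for partial onset dates, cross-referring to SAP Section 9.5 if its redacted text already has one. This matters most after Day 42, when scheduled queries are 126 days (168 − 42) and then 168 days (336 − 168) apart.
4. At least one overall TEAE summary by period and arm, including severity and relationship, and SOC/PT tables for the on-treatment period.
5. Subjects still under observation as the follow-up denominator, described as a post-randomisation subset and not as a randomised comparison.

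Keep all whole-study AE and SAE tables, so that late events stay visible.

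The cost is SAP wording, a few extra tables, derivation of last dose and of the follow-up denominator, the partial-date rule, and a justification of the interval. No new data are needed: Protocol Section 9.1 already requires onset dates, and the planned exposure duration already calls for the end of dosing.

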13.2 Prior and Concomitant Medications

Table 3 describes the classification of prior and concomitant medications.

Table 3 Classification of prior and concomitant medications			
[Redacted]	[Redacted]	[Redacted]	[Redacted]
[Redacted]	[Redacted]	[Redacted]	[Redacted]
[Redacted]	[Redacted]	[Redacted]	[Redacted]
[Redacted]	[Redacted]	[Redacted]	[Redacted]

[figure not shown]
14 Subgroup Analyses

Appendix 1 Schedule of Visits and Measurements

Procedure	Screen/ Visit 1 Day 1	Day 2-6	Visit 2 Day 7 ±2	Day 8-13	Visit 3 Week 2 Day 14 ±3	Day 15-27	Visit 4 Week 4 Day 28 ±4		Visit 5 Week 6 Day 42 ± 3	Visit 6 Week 24 Day 168 ±7	Visit 7 Week 48 Day 336 ±7	ET
							Visit 4a	Visit 4b (+3 days of 4a)				
							Pre- CAE®	Peri- CAE®	Schirmer's Test Evaluation			
Informed consent/HIPAA	X											
Demographics	X											
Medical history, prior medication(s), ocular history and updates	X											
Eligibility criteria	X											
Urine pregnancy test	X ¹						X ¹				X ¹	X ¹
OSDI® questionnaire	X											
Eye Dryness Score (EDS)	X		X		X		X	X ⁴				X
Ocular Discomfort Scale	X						X	X ⁴				
BCVA	X ²		X		X ²		X					X
Slit lamp biomicroscopy	X ²		X		X ²				X	X	X	X
Corneal fluorescein staining	X											X
Schirmer's test	X ²				X							
Schirmer's test with cotton swab Stimulation	X											
Intranasal examination	X ²		X						X	X	X	X
Randomization	X											
Administer investigational drug / Placebo	X ³	X		X	X ³	X		X				
Diary Completion		X		X		X						

Appendix 2 Analysis for secondary efficacy endpoints with multiple imputation

[Redacted text block]

[Redacted text block]

[Redacted text block]

[Redacted text block]

[Redacted text block]

1. Exhibit 1. Sample SAS code for assessing missing data patterns
